### 5.2.2 Secondary outcome analysis

#### HbA1c based

For the HbA1c 12-week outcome, an ANCOVA model will be used, with trial arm effect as the focus, with adjustment for baseline HbA1c and the other baseline variables included in the minimisation allocation algorithm as covariates.

For the HbA1c-based [yes/no] variables, logistic regression models will be used. For each model, trial arm effect will be the focus, with adjustment for the baseline HbA1c and the other variables included in the minimisation allocation algorithm as covariates.

#### Sensor-based

The respective sensor-based measures obtained during the last 2 weeks of the 24-week randomised interventions contrasting the flash-glucose against the SMBG will be compared

using ANCOVA. Analysis will be adjusted for baseline sensor values obtained during blinded run-in period, the baseline HbA1c and the other variables included in the minimisation allocation algorithm. Analysis will also be repeated for day and night-time period (the interval from 7.00 to 23:00 defines day-time period; 23:00 to 07:00 am defines the night-time period).

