	during a remote video consultation supported by online education material developed by Diabetes Technology Network. Participants will be advised to use flash glucose monitoring continuously for the next 24 weeks.
2. Self-monitoring of blood glucose	Masked FSL2 will be applied for two weeks, during the last two weeks of control period. Education will focus on using finger-stick measurement for treatment optimisation with education provided either in person or during a remote video consultation supported by online educational material such as Bertie Online(www.bertieonline.org.uk). Blinded FSL2 will be posted to participants where necessary for self-insertion with relevant advice.
End of 24 week assessments	
 - A blood sample will be taken for measurement of HbA1c using the local laboratory (face to face clinic) or a home HbA1c where the participant will collect a blood sample using a self-test kit and send in a pre-paid envelope to a central or third party external laboratory. - Validated questionnaires as described before evaluating quality of life, mood, needle burden, disordered eating, diabetes distress and diabetes treatment satisfaction will be completed either during face to face clinics or by postal delivery for virtual consultations. 
Additional questionnaire for those in the FSL2 arm exploring expectations and experience of using FSL2 during the study will also be administered.

Procedures for safety monitoring during trial	Standard operating procedures for reporting all adverse events will be in place.

3 Summary

FreeStyle Libre 2 (FSL2) is a novel glucose monitoring device (Flash glucose) in the form of a disc worn on the arm for 14 days and a hand-held reader which is designed to largely replace the recommended 4-10 painful finger-stick blood glucose tests required each day for the self-management of type1diabetes. The purpose of this study is to determine whether flash glucose monitoring with FSL2 device will improve HbA1c over a 24-week period compared to self-monitoring of blood glucose in adults and adolescents (16 years or older) with sub-optimally controlled (HbA1c 7.5% to 11%) type 1 diabetes.

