9.7 Visit 6: (+22 weeks since randomisation): Finger-stick glucose monitoring arm only

Participants randomised to finger-stick glucose monitoring arm will have an extra visit 10 weeks after visit 5 to insert a blinded glucose sensor for data capture. Participants who join the trial by virtual consultation will receive a Blinded FSL2 pro sensor and reader by post for self-insertion with relevant advice. At the end of the two weeks the participant can return the items to the research team by pre-paid postal services.

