## 2.7 Timing of outcome assessments

Table 1: Schedule of study visits when participant is randomised to flash glucose monitoring intervention (intervention group).

Visit/contact	Flash glucose monitoring - description	Time since randomisation	Start relative to previous/next Visit / Activity*
Visit 1	Recruitment & Screening visit: Consent HbA1c, baseline bloods, questionnaires	-2 to -3 weeks	-
Visit 2	Blinded flash glucose monitor insertion	-2 weeks	Within 1 to 2 weeks of Visit 1. Can coincide with Visit 1
Visit 3	Adherence assessment & Randomisation  Flash-glucose monitoring initiation - Training, education & competency assessment	0 weeks	After 2 weeks of Visit 2
Visit 4	Review data /optimisation and use of study devices. Data download & collect participant diary	+4 weeks	After 4 weeks of Visit 3
Visit 5	Review data /optimisation. Data download - HbA1c. - Collect participant diary	+12 weeks	After 8 weeks of Visit 4
Visit 6	Not applicable in this arm	+22 weeks	-
Visit 7	End of Flash-glucose monitoring intervention arm - HbA1c - Questionnaires - Data download - Collect participant diary	+24 weeks	12 weeks after Visit 5

\* Each study visit can be scheduled with +/- 2 weeks of the planned visit date.

Table 2: Schedule of study visits when participant is randomised self-monitoring of blood glucose

Visit/contact	Self-monitoring of blood glucose - description	Time since randomisation	Start relative to previous / next Visit / Activity*
Visit 1	Recruitment & Screening visit: Consent HbA1c, baseline bloods, questionnaires	-2 to -3 weeks	-
Visit 2	Blinded flash glucose monitor insertion	-2 weeks	Within 1 to 2 weeks of Visit 1. Can coincide with Visit 1
Visit 3	Adherence assessment & Randomisation Self- monitoring of glucose initiation - Education Data download	0 weeks	After 2 weeks of Visit 2
Visit 4	Review data /optimisation Collect participant diary	+4 weeks	After 4 weeks of Visit 3
Visit 5	Review data /optimisation. - HbA1c - Collect participant diary Data download**	+12 weeks	After 8 weeks of Visit 4
Visit 6	Blinded flash glucose monitor insertion (Extra visit in this arm)	+22 weeks	After 10 weeks of Visit 5
Visit 7	End of self-monitoring intervention arm - HbA1c. - Questionnaires - Collect participant diary	+24 weeks	2 weeks after Visit 6

\* Each study visit can be scheduled with +/- 2 weeks of the planned visit date.

\*\*This data download will be for self-monitoring of blood glucose/pump data.

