#### 3.2 Adherence and protocol deviations

##### 3.2.1 Adherence

During Visit 3, participant's adherence / tolerance of using the flash-CGM over the preceding 14 days will be assessed. To proceed with the study participant should have worn the blinded glucose monitoring device for at least 10 days during last 14 days of run-in period. If the participant fails to demonstrate adherence or develops any significant allergy or intolerance to the glucose sensor, the participant will be removed from the study.

The number and percentage of participants failing to demonstrate adherence and not wearing the blinded glucose monitoring device for at least 10 days will be presented in a table.

During the trial, intervention adherence data will be collected and analysed as part of the process evaluation and will also be considered in a sensitivity analysis of the primary outcome measure using Complier Adjusted Causal Estimation (see Section 5.2.3). During Visit 7, participant's adherence / tolerance at the control group of using the flash-CGM over the preceding 14 days will also be assessed. Participants' adherence will be defined as wearing the blinded glucose monitoring device for at least 10 days during last 14 days of Visit 7. The number and percentage of participants at the control group failing to demonstrate adherence and not wearing the blinded glucose monitoring device for at least 10 days will be presented in a table. The percentage of time wearing the glucose sensor alongside mean glucose sensor usage will also be recorded for participants in the flash-glucose monitoring arm.

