#### **3.3 Analysis populations**

All efficacy and safety analyses will be conducted following the ITT principle where all randomised participants are analysed in their allocated treatment group whether or not they receive their randomised treatment according to the protocol.

The primary outcome analysis will be conducted based on a complete-case analysis approach unless there is more than 10% of participants who have missing HbA1c at 24 weeks (or more than a 10% difference between missing data percentages in the two arms), in which case multiple imputation will be used in order to implement a more complete ITT analysis of the substantive Analysis of Covariance (ANCOVA) model (otherwise this will be performed as a sensitivity analysis, with a complete case analysis used as the primary analysis).

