### 5.3 Missing data

Should we have more than 10% missing HbA1c at 24 weeks (or more than a 10% difference between missing data percentages in the two arms), multiple imputation will be used in order to implement a more complete ITT analysis of the substantive ANCOVA model. The imputation model will include baseline and 12-week HbA1c, all the baseline variables used in the outcome model and any other recorded variables found to be predictive of missing the 24-week outcome in exploratory analyses (via a logistic regression model, with terms included using a 10% significance level). A minimum of 50 imputations will be performed, although this will be increased if the percentage of missing data is greater than expected. We will perform multiple imputation by chained equations (MICE).

Complete cases analyses will be implemented for all secondary outcomes. Should we have up to 30% missing items for any subscale (or overall questionnaire if no subscales), the missing item will be imputed by the mean response of the rest items completed within participant for that particular subscale. If more than 30% missing items the response to this subscale will be set to missing, as will be the overall response of the questionnaire.

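### End-of-study sensor data in the FSL2 arm exist only for participants still using the device, so the complete-case sensor comparison is not ITT and needs a planned missing-data sensitivity analysis

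*SAP*

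**What the plan says.** Four provisions bear on this.

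- **Outcome window.** SAP 5.2.2 (Sensor-based) takes as outcomes "The respective sensor-based measures obtained during the last 2 weeks of the 24-week randomised interventions" and compares them by ANCOVA, adjusted for the run-in sensor value, baseline HbA1c and the other minimisation factors.
- **Source of the data.** For controls, the Protocol synopsis says: "Masked FSL2 will be applied for two weeks, during the last two weeks of control period". Protocol 9.7 adds that they "will have an extra visit 10 weeks after visit 5 to insert a blinded glucose sensor for data capture". For the FSL2 arm, the visit table in SAP 2.7 marks Visit 6 as "Not applicable in this arm". That arm's use is tracked instead (SAP 3.2.1): "The percentage of time wearing the glucose sensor alongside mean glucose sensor usage will also be recorded for participants in the flash-glucose monitoring arm".
- **Missing data.** SAP 5.3: "Complete cases analyses will be implemented for all secondary outcomes". Multiple imputation is planned only for 24-week HbA1c.
- **Analysis population.** SAP 3.3: "All efficacy and safety analyses will be conducted following the ITT principle where all randomised participants are analysed in their allocated treatment group".

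SAP 1.2.2 names sensor time below 3.0 mmol/l as part of the safety objective. Under Protocol 9.9, participants withdrawn on certain grounds, including non-adherence and sensor allergy, may be invited to give HbA1c and questionnaires. Sensor data are not mentioned. Neither document plans a masked sensor for FSL2 participants who have stopped the device.

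**The concern.** In one arm, having the outcome requires still using the assigned treatment; in the other it does not. A participant who gives up FSL2 before week 22 has no week 22-24 sensor record, and the complete-case rule then removes that person. No single sentence says so; it follows from putting the outcome window, the visit schedule and the missing-data rule together.

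The sensor comparison is then between continuing FSL2 users and controls who wore the masked sensor. If stoppers do worse than continuers, the FSL2 arm's mean is flattered. At stake are time in range and the other sensor metrics, including the sensor part of the safety objective, all of which would be reported under an ITT heading.

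**Working it through.** **1. The plan's own figure.** The only sample-size figure concerns HbA1c: 64 per arm for a difference of 0.4% with SD 0.8%. The noncentral t gives power 0.801 at 64 per arm, and 128/0.85 = 150.6 against 150 randomised. Both reproduce. No power, stopping rate or missing-data figure is given for any sensor outcome, so everything below is illustrative.

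**2. Formula.** Let d be the share of the FSL2 arm without end-of-study sensor data, and gap the mean outcome of those with data minus that of those without, signed so that positive means better. The all-randomised FSL2 mean is (1 − d) × continuers + d × stoppers. Complete case reports the continuers' mean, so it is too favourable by d × gap. If controls lose a share c with the same gap, the net bias is

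bias = (d − c) × gap.

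**3. Inputs.** Reference values for d, none of them specific to this trial:

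- 2.1% = 7/328, the device-related withdrawals in the largest trial of the earlier device (Protocol 4.3 and 4.7). The split by arm is not given, so the device-arm rate may be higher.
- 12.9% = 4/31, from a small cohort in which 27 continued (Protocol 4.4).
- 15%, the overall attrition allowance (SAP 2.3), which is not a device-stopping rate.
- 25%, families of paediatric users outside a trial (Protocol 4.5).

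Gaps of 0.5 and 1.0 SD are assumptions.

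**4. Size with no control loss (c = 0).** The rejection rate is that of a two-sided 5% test when the true all-randomised difference is zero. It uses 75 per arm before loss, the normal approximation and no baseline correlation.

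| d | Bias, gap 0.5 SD | Rejection rate | Bias, gap 1.0 SD | Rejection rate |
|---|---|---|---|---|
| 2.1% | 0.011 SD | 5.0% | 0.021 SD | 5.2% |
| 12.9% | 0.065 SD | 6.7% | 0.129 SD | 11.9% |
| 15% | 0.075 SD | 7.2% | 0.150 SD | 14.2% |
| 25% | 0.125 SD | 10.9% | 0.250 SD | 29.4% |

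Example, d = 15% and gap 0.5 SD: the standard error is √(1/63.75 + 1/75) = 0.170, so the shift is 0.075/0.170 = 0.44 standard errors.

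**5. In percentage points of time in range.** An assumed gap of 5 to 15 points gives 0.1 to 0.3 points at d = 2.1% and 0.75 to 2.25 points at d = 15%.

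**6. With control loss.** At d = 15% and gap 0.5 SD, the bias is 0.050 SD if c = 5%, 0.025 SD if c = 10% and zero if c = 15%. At d = 2.1% and c = 10% it changes sign: (0.021 − 0.10) × 0.5 = −0.039 SD.

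**7. Simulation check.** Assume an 8-point effect on time in range in users, none in stoppers, SD 15, a correlation of about 0.75 with 24-week HbA1c, and random stopping in the FSL2 arm only (1,500 trials of 150 per setting). At 5%, 10% and 15% stopping:

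- All-randomised effect: 7.68, 7.20 and 6.82 points.
- Complete case: 8.09, 8.01 and 8.01, an excess of 0.41, 0.81 and 1.19 points. This agrees with d × 8 = 0.40, 0.80 and 1.20, and is 5%, 11% and 17% of the all-randomised effect.
- Multiple imputation: 7.90, 7.64 and 7.47, an excess of 0.22, 0.44 and 0.65. About 45% of the bias is removed.

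**The case against.** The strongest reply is that controls lose data too. A reader might infer that the analysis sets continuing users against all controls. The documents do not support that: masked sensors can be posted for self-insertion and return (Protocol 9.7), SAP 3.2.1 expects some controls to wear the sensor for fewer than 10 of the last 14 days and will tabulate them, and controls who withdraw also disappear. This stands, and it is why the bias depends on d − c.

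Second, every participant has passed a run-in requiring at least 10 of 14 days' wear, and the cited trial's withdrawal figure is low. At about 2% stopping the bias is negligible. This stands as to size.

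Third, SAP 3.3 can be read as defining ITT by allocated group, and for the primary outcome it openly treats imputation as the more complete version. That is fair, but the same sentence refers to all randomised participants, and the sensor analysis cannot deliver that.

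Fourth, the plan has related safeguards. Missed sensor downloads are a listed deviation category (SAP 3.2.2), wear is reported (SAP 3.2.1), severe hypoglycaemia is tabulated whether or not sensor data exist (SAP 5.2.2), and SAP 5.2.3 permits extra sensitivity analyses, including on key secondary outcomes, at the team's discretion. These describe the problem in part. None specifies an analysis for missing sensor data.

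**Conclusion.** The point holds as one of labelling and of an unplanned sensitivity analysis. For the sensor outcomes, including time below 3.0 mmol/l, the plan compares continuing FSL2 users with controls who wore the masked sensor, and this does not meet the ITT principle of SAP 3.3.

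The size cannot be fixed from the documents, because d, c and the gap are all unstated. With no control loss and an assumed gap of 0.5 SD, the bias runs from about 0.01 SD at 2% stopping to 0.075 SD at 15%; it vanishes if both arms lose data equally with the same gap. It probably favours FSL2 for time in range, on the assumption that more FSL2 participants lack data and that stoppers do worse.

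A reader might also infer that the hypoglycaemia result is biased towards the device. That is not supported. If stoppers run higher glucose, they may spend less time below 3.0 mmol/l, and dropping them could then count against FSL2. The direction for that outcome is unknown. The primary HbA1c analysis is not affected by this mechanism.

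**What to change.** In SAP 5.3, keep the complete-case sensor result and add the following for time in range and time below 3.0 mmol/l:

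1. A sensitivity analysis by multiple imputation, using arm, run-in sensor value, baseline, 12-week and 24-week HbA1c, and the minimisation factors.
2. A version that imputes FSL2-arm stoppers from the control arm.
3. The number with sensor data and the reasons for absence, by arm.
4. A description of the complete-case result as a comparison among participants with sensor data, not as ITT.

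This needs no new visits or data, only more analysis work. Both versions rest on missing-data assumptions that cannot be tested. Imputation alone is a partial remedy: it removed only about 45% of the bias in the simulation above, and it depends on 24-week HbA1c, which some withdrawn participants may not provide. The control-based version addresses stopping more directly, but its performance was not simulated. For these reasons both are proposed beside the complete-case result, not in place of it.

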14.2.2 Secondary Outcomes

HbA1c based

For the HbA1c 12-week outcome, an ANCOVA model will be used, with trial arm effect as the focus, and with adjustment for baseline HbA1c and the other baseline variables included in the minimisation allocation algorithm as covariates.

For the HbA1c-based [yes/no] variables, logistic regression models will be used. For each model, trial arm effect will be the focus, with adjustment for the baseline variables included in the minimisation allocation algorithm (including baseline HbA1c category) as covariates.

Sensor-based

The respective sensor-based measures obtained during the last 2 weeks of the 24-week randomised interventions contrasting the flash-glucose against the SMBG will be compared using independent-samples statistical techniques. For any non-normally distributed (substantially skewed) measures, transformation or nonparametric analyses will be used. Where possible, analysis will be adjusted for baseline sensor values obtained during blinded run-in period and the baseline variables included in

the minimisation allocation algorithm. Analysis will also be repeated for day and night-time period (the interval from 7.00 to 23:00 defines day-time period; 23:00 to 07:00 am defines the night-time period).

Non-sensor based clinical

For the insulin dose data, independent-samples statistical techniques will again be used. For any non-normally distributed (substantially skewed) measures, transformation or nonparametric analyses will be used. Analysis will be adjusted for the baseline value of the outcome measure and the baseline variables included in the minimisation allocation algorithm.

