### 1.2.2 Study Objectives

The primary objective is to assess the clinical efficacy of flash glucose monitoring with FSL2 device relative to that with self-monitoring of blood glucose on glycated haemoglobin A1c (HbA1c).

Secondary clinical and psychosocial objectives are, respectively:

- to assess the clinical efficacy of flash glucose monitoring with FSL2 device relative to that with self-monitoring of blood glucose on sensor-based glucose metrics (e.g. time spent in target glucose range 3.9 to 10 mmol/L).
- to evaluate the participants' responses in terms of quality of life, diabetes related distress, diabetes treatment satisfaction, low mood, needle burden and disordered eating behaviours using validated questionnaires.

The safety objective is to evaluate time spent in hypoglycaemia (sensor glucose levels < 3.0 mmol/l and other sensor based biochemical hypoglycaemia) and number of episodes of severe hypoglycaemia with FSL2 and self-monitoring of blood glucose.

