### **4 TRIAL POPULATION**

#### **4.1 Screening data**

The number of patients being screened will not be reported due to discrepancies with how screening data is being collected across the different sites. The number of patients who are assessed for eligibility will be reported.

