### **Sensor based**

1. Time spent in the target glucose range between 3.9 to 10.0 mmol/l (70 to 180mg/dl).
2. Time spent below target glucose (<3.9mmol/l) (<70mg/dl)
3. Time spent above target glucose (10.0 mmol/l) (180 mg/dl)
4. Average glucose levels
5. Standard deviation glucose levels
6. Coefficient of variation glucose levels
7. The time with sensor glucose levels:
  - < 3.5 mmol/l (63 mg/dl)
  - < 3.0 mmol/l (54mg/dl)
  - < 2.8 mmol/l (50 mg/dl)
8. The time with sensor glucose levels in the significant hyperglycaemia (glucose levels > 16.7 mmol/l) (300mg/dl)
9. AUC of glucose below 3.0mmol/l (54mg/dl)
10. Glucose management Indicator

All the sensor-based metrics will also be analysed separately for daytime (7:00-23:00 hours) and night-time (23:00-7:00 hours) in addition to the overall period.

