### **Non-sensor based secondary patient-reported (psychosocial)**

1. T1-DDS: mean-item score
2. EQ-5D-5L (This outcome will not be covered in the SAP but instead will be included in the Health Economics Analysis Plan.)
3. PHQ-9 total score
4. D-FISQ total score
5. DEPS-R total score

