## 5.2 Analysis methods

All 12-week and 24-week outcome data will be presented descriptively, both overall and within treatment group, using mean (SD), median (IQR) or frequency (percentage), as appropriate. Mean (SD) change of HbA1c will also be presented overall and by treatment group. All statistical tests will use a 2-sided significance level of 5% (unless otherwise specified), and all confidence intervals will be presented at a level of 95% and will be two sided.

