### **Non-sensor based clinical**

For the insulin dose data, ANCOVA will again be used. Analysis will be adjusted for the baseline value of the outcome measure, the baseline HbA1c and the other variables included in the minimisation allocation algorithm. This analysis will be repeated to compare the two intervention groups for the insulin dose data obtained both at 12 weeks and at 24 weeks following randomisation.

Safety data, including number of severe hypoglycaemia events and number of ketone-positive hyperglycaemia, will be tabulated for all participants, including drop-outs and withdrawals, irrespective of whether CGM data are available and irrespective of whether closed-loop was operational. Severe hypoglycaemic events and ketone-positive hyperglycaemia will be tabulated in each treatment group.

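### Should the SAP carry a rule for skewed sensor and insulin measures, because Protocol 14.2.2 has one and SAP 5.2.2 does not?

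*SAP*

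**What the plan says.** Protocol 14.2.2 compares sensor and insulin-dose measures by unspecified independent-samples techniques and adds, once for each group of measures: "For any non-normally distributed (substantially skewed) measures, transformation or nonparametric analyses will be used". It gives no threshold for skewness and names no transformation or test.

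SAP 5.2.2 is more specific. Sensor measures from the last two weeks are compared "using ANCOVA. Analysis will be adjusted for baseline sensor values obtained during blinded run-in period", together with baseline HbA1c and the other minimisation factors. For insulin: "For the insulin dose data, ANCOVA will again be used", at 12 and at 24 weeks. Neither paragraph mentions skewness or a scale.

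For description, SAP 5.2 says "All 12-week and 24-week outcome data will be presented descriptively, both overall and within treatment group, using mean (SD), median (IQR") or frequency, as appropriate. Protocol 14.2 has the same latitude. Protocol 14.2 also provides for a full, detailed SAP, approved by the TSC after review by the TMG, TSC and IDMC.

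**The concern.** If a measure is substantially skewed, the two documents appear to call for different analyses of it. Several sensor metrics are bounded at zero and likely to be skewed: time below 3.9, 3.5, 3.0 and 2.8 mmol/l, time above 16.7 mmol/l, and AUC below 3.0 mmol/l. One of them matters for safety: "The safety objective is to evaluate time spent in hypoglycaemia (sensor glucose levels < 3.0 mmol/l". The metrics are also multiplied by period: "All the sensor-based metrics will also be analysed separately for daytime (7:00-23:00 hours) and night-time (23:00-7:00 hours") as well as overall.

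The silence is noticeable because the SAP does account for other omissions. Screening counts "will not be reported due to discrepancies with how screening data is being collected across the different sites", and for the EQ-5D-5L it says "This outcome will not be covered in the SAP but instead will be included in the Health Economics Analysis Plan".

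Two things would be at stake. The final analysis could depart from the protocol on secondary and safety-related outcomes without a recorded reason. And a table could show equal medians, or zero against zero, beside a significant test of means.

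**Working it through.** **1. How many comparisons.** SAP 5.1.2 lists 12 sensor metrics, counting the three thresholds in item 7 separately. The Glucose Management Indicator is not among the 11 in Protocol 10.2.2, so no protocol rule conflicts with it. The ceiling is 11 × 3 periods = 33. Insulin adds up to 4 measures × 2 time points = 8, although the protocol's insulin paragraph gives no time points. Both are ceilings, because the rules differ only for measures that prove substantially skewed.

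**2. The plan's own figure.** The sample size rests on HbA1c alone. With a standardised effect of 0.4/0.8 = 0.5 and 64 per arm, the noncentrality is 0.5 × √(64/2) = 2.83 and the two-sided 5% t-test has power 0.801. The stated 128 reproduces. No figure is stated for the skewed secondary measures, and none in the documents depends on this point.

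**3. Does the scale matter?** The documents give no SD or share of zeros for these metrics in this population, so the inputs are assumptions: 64 per arm, lognormal values, baseline correlation 0.5 and log-SD 0.5 to 1.5. ANCOVA adjusts for baseline and is run on the raw scale, on log(x + 0.1) and on ranks. For zeros, the lowest 0–60% of values are set to zero in both arms.

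The 38% effect is the reduction in time below 3.9 mmol/l that Protocol 4.3 cites from the trial in well-controlled type 1 diabetes. One orientation point for the log-SD comes from the type 2 diabetes trial in the same section (224 participants; 0.47 ± 0.13 h/day; a 43% reduction), reading ± as a standard error and assuming 112 per arm:

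- mean = 0.47/0.43 = 1.09 h/day
- SD = 0.13/√(2/112) = 0.97
- CV = 0.97/1.09 = 0.89
- log-SD = √ln(1 + 0.89²) = 0.76

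Type I error was about 3–6% on all three scales. Power (%) at log-SD 1.0, raw/log/rank:

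| True zeros | Uniform 38% reduction | Values capped at the control 75th centile |
|---|---|---|
| none | 65/87/85 | 58/21/11 |
| 20% | 59/45/70 | 55/11/11 |
| 50% | 43/15/27 | 48/9/12 |
| 60% | 34/11/16 | 46/8/11 |

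For a uniform effect without zeros, the raw scale gives up 87 − 65 = 22 points to the log (about 6 at log-SD 0.76). In every other row and column except 20% zeros with a uniform effect, where ranks lead, the raw scale is ahead. With zeros, the log results depend on the constant added: at 20% zeros and a uniform effect, log power is 22, 43, 63 and 68% for constants of 0.01, 0.1, 0.5 and 1.0 in a separate run, against 59% raw. So restoring the protocol's transformation option would also require choosing a constant.

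**4. Median shown, mean tested.** With a uniform 38% reduction and 0–20% zeros, a significant raw benefit goes with an FSL2 sample median no lower than control in 2.5% of trials or fewer. Under the cap without zeros the true median does not move, while the mean falls 22, 33 and 57% at log-SD 0.76, 1.0 and 1.5. The mismatch rate is then 26, 32 and 39%. With 60% zeros both sample medians are zero in 86–88% of trials.

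**5. What the SAP already yields.** Read plainly, as for HbA1c in the same section, the model is untransformed ANCOVA. Its effect measure is the adjusted mean difference, and SAP 3.1 and 5.2 set 95% confidence intervals. Medians, where tabulated, would normally stand beside that estimate.

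**The case for a change.** The strongest case for acting is that the conflict in wording is certain and a sentence would close it. Skewness was in the SAP authors' view, because SAP 4.5 sets a skewness criterion for baseline tables. As SAP 5.2.2 names no scale, an analyst might cite either document and choose after seeing the data. Section 5.2 also adapts the description to skewness while the test stays fixed.

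Part of this stands. The reason is unwritten, and recording one would be good housekeeping. The raw scale has a limit too: under the cap, coverage of its 95% interval is about 94% at log-SD 0.76, 90–93% at 1.0 and 82–83% at 1.5. It is not uniformly reliable in the extreme tail of these assumptions.

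The rest is weaker. The SAP does not always explain its departures, so this silence is not singular. Protocol 14.2.2 compares severe hypoglycaemia and ketosis by generalised estimating equations, while SAP 5.2.2 only tabulates them. Protocol 14.2.2 adjusts the yes/no HbA1c models for the baseline category, where the SAP names baseline HbA1c. The freedom to choose after seeing data lies mostly in the protocol's open-ended rule, and naming one model narrows it. The zero-against-zero table needs about 60% zeros, for which the documents offer no support. SAP 5.2 does not require medians to be shown alone.

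**Conclusion.** The SAP leaves out a protocol rule without saying why, but the plan needs no change. Protocol 14.2 delegates the detail, the rule itself could not be applied without further choices, and covariate-adjusted ANCOVA for every measure is a legitimate way to make them. The obvious remedy, a paragraph confirming the untransformed scale with the adjusted mean difference, would alter no test. Replacing that scale with logs or ranks would be a trade-off, with a gain under a uniform effect and few zeros and a loss when the effect lies in the upper tail. The mismatch between medians and means is met by ordinary reporting of the model estimate with its interval.

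The reach is at most 33 sensor comparisons and up to 8 insulin comparisons, all secondary and without multiplicity adjustment, and only where skewness is substantial. The power, coverage and mismatch figures rest on assumed lognormal data, a baseline correlation of 0.5 and assumed shares of zeros. No numerical claim is made for insulin dose. The conclusion on the documents does not depend on those figures, and the primary analysis is untouched.
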